#### Follow-ups

Follow-up 1 - Baseline+ 12 weeks

Follow-up 2 - Baseline + 6 months

Participants will be sent up to 3 email reminders for non-response to the follow-up questionnaires.

#### 6.7 Selection of outcome measures for phase 2

Phase 2 primary and secondary outcome measures will be selected from the analysis of phase 1 quantitative and qualitative results. Following phase 1 analysis, the multidisciplinary ADAPT study team will meet to decide which intervention(s) will proceed to phase 2 and which outcome measures to select for phase 2. The selection criteria will include (with most weight given to patient views on importance):

- 1. Acceptability and perceived importance and relevance of each measure to patients. These will be assessed quantitively by questions on the survey about each instrument, and qualitatively during interviews. Any measures that are rated as unacceptable or irrelevant by >25% of participants will be excluded. Participants will be asked to rank the measures in terms of importance to them and a mean score calculated. The top 3 scoring outcome measures will be discussed, taking into account additional patient views from interviews, team views and sensitivity as detailed below to select one measure for the primary outcome measure. Other measures will be considered for inclusion as secondary outcomes, by considering the ordering of patient scores, and patient willingness to complete different lengths of follow-up surveys. A minimum of one phase 1 outcome measure will be excluded for phase 2.
- 2. Sensitivity of each measure to change by psychosocial interventions. Short-term effectiveness of each intervention will be measured by using the within-person change from baseline to follow-up one, for each phase 1 instrument.

We will be trialling The ADAPT instrument (Appendix 1), a new disease adapting tool which includes 21 items incorporating: disease acceptance, coping, control, empowerment, knowledge, participation in life and satisfaction with life and medical care. Its validity and reliability will also be tested in this study. The factorial structure of this tool will be investigated using exploratory and confirmatory factor analysis, while its reliability will be tested using the Cronbach's alpha coefficient. For the validation of this tool, we will also calculate its correlation with other previously validated tools (The Connor Davidson resilience scale and the PHQ depression scale), using the Pearson correlation coefficient. If acceptable and considered to be relevant to patients, ADAPT (personal and social domains) will be considered as a primary or secondary outcome. EQ-5D-5L will be a secondary outcome regardless of phase 1 results due to the importance to the NHS. FACIT-F (unless unacceptable to >25% of respondents) will be a (primary or secondary) outcome measure for the stage two physical activity trial as fatigue is a key target of this aspect of the trial to improve.

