# 4 Study Synopsis

Study title	The ADAPT study (Adapting, Disease self-management and							
	Acknowledgement through Psychosocial Targeted interventions)							
Short title	The ADAPT study							
Principal	[name] and [name]							
Investigators								
Chief Investigators'	University of Cambridge							
employing Institution								
Study sponsor	University of Cambridge							
Funder	LUPUS UK and The Lupus Trust							
	·							
Study Duration	3 years (over 2 phases)							
Participants								
Sample size	Phase 1							
	N=120 (n=30 in each of the 3 intervention groups of text messaging							
	intervention, listening support (The Wren Project) and the online physical							
	activity course (Flexifit Pilates) and n=30 in control.							
	Phase 2							
	N=800 (approximately)							
	Numbers dependent on which interventions progress to phase 2, and sample size calculations informed by phase 1. Provisional estimates of N=100 for online physical activity, N=100 for The Wren support, N= 300 for							
	text messaging support and N=300 control.							
	Process and acceptability evaluation interviews with phase 1 participants will take place until theoretical saturation (the point at which no new concepts are generated) is reached. Estimated 15 for each intervention group.							
Objectives	Aim							
	To assess the acceptability, feasibility and effectiveness of methods of remote psychosocial support for SARDs patients. For the interventions trialled (if effective and acceptable) to be incorporated as an adjunct to usual care.							
	Objectives							
	To trial multiple quality of life and mental health measures to determine the most appropriate primary and secondary outcomes for phase 2.							
	To test processes to inform phase 2 effectiveness trial.							
	To develop and trial our own ADAPT instrument to more accurately							

	reflect, measure and monitor SARD patient personal, social and medical satisfaction.  • To assess the acceptability (phase 1) and effectiveness (phase 2) of remote psychosocial interventions on the mental health, wellbeing, self-esteem, resilience, loneliness and disease acceptance of patients with systemic autoimmune rheumatic diseases.

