#### 6.7 Analysis and outcome measures

Qualitative – The qualitative data will be analysed using thematic analysis and NVivo12 for managing and coding data and follow the criteria for reporting qualitative research (COREQ). Briefly, the stages of analysis involved in our qualitative research involves an inductive-deductive process, including: (i) immersion in the data where transcripts and subsequent coded sections are repeatedly read and discussed by multiple team members to improve reliability, and ensure multiple perspectives and possible interpretations are represented; (ii) a coding (classification) scheme is developed, trialled, discussed and refined, and each line of qualitative data is coded; and (iii) participant extracts for each code are combined. The key themes emerge directly from the data and team discussions, including with multiple patients and clinicians.

Consideration of deviant cases, member checking, triangulation of quantitative and qualitative results and multiple perspectives will be conducted to improve validity.

Quantitative - Transferral of online data from Qualtrics online survey platform and manual data entry, data cleaning, recoding and generation of new variables onto SPSS V26.

Descriptive statistics (means, medians, Interquartile range (IQR), modes and range for continuous data and percentages for categorical data) will be used to describe the demographic, survey and trial data. Contingency tables will be used to describe the multivariate frequency distribution of categorical variables. Bar charts, histograms and boxplots will be used additionally to the above-mentioned statistics and in order to ensure the results are easily accessible to patients, clinicians and policy makers. We will assess the association between variables of interest using Pearson correlation coefficient, T-tests, Wilcoxon-Mann Whitney tests, Chi-Square tests and Kruskal Wallis tests. Regression models will be used to assess the effect of multiple variables on specific outcomes. The within-person change from the baseline to follow-ups and the primary endpoint will also be investigated for each outcome measure. Multiple regression analysis will be used to test differences between groups on multiple measures.

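### Section 6.7 defines phase 1 short-term effectiveness, and each measure's sensitivity, as within-person change without a contrast to the randomised control arm

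*Protocol*

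**What the plan says.** The protocol's section 6.7 on selecting outcome measures for phase 2 sets two criteria. The first is acceptability and importance to patients. The second is headed "Sensitivity of each measure to change by psychosocial interventions", and its estimator is fixed in the next sentence: "Short-term effectiveness of each intervention will be measured by using the within-person change from baseline to follow-up one, for each phase 1 instrument". No comparison arm is mentioned.

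The result is used in choosing the primary outcome. The three measures that patients rank highest go to a discussion that takes account of further patient views from interviews, "team views and sensitivity as detailed below to select one measure for the primary outcome measure". The criteria as a whole are applied "with most weight given to patient views on importance".

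Section 6.3 adds that exact phase 2 sample sizes will be worked out from what phase 1 indicates about effectiveness.

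Phase 1 does have a randomised control. The synopsis gives "N=120 (n=30 in each of the 3 intervention groups of text messaging" and, after the other two interventions, "n=30 in control". Section 6.3 describes block randomisation to an intervention or control.

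The section on analysis and outcome measures (also numbered 6.7) says: "The within-person change from the baseline to follow-ups and the primary endpoint will also be investigated for each outcome measure". It then plans multiple regression and a range of tests between groups. It does not say which phase these serve, and it does not tie them to outcome selection or to sample size.

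**The concern.** Sensitivity to change caused by an intervention is a causal quantity. Change from baseline to 12 weeks inside one arm does not isolate it. That change also contains the natural course of the disease, the effect of answering the same questionnaires twice, and possibly regression to the mean among people who volunteered for support. The randomised control arm is there to remove change of this kind, and the rule as written does not use it.

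There is a second difficulty. The instruments have different scales; the ADAPT tool, for example, uses 0-100 sliders. Raw changes cannot be ranked against one another without standardisation, and none is stated.

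Two decisions are exposed. A measure that drifts for reasons unrelated to the intervention could look responsive and gain ground in the choice of primary outcome. And an effect that includes drift, if carried into the phase 2 calculation, would make that trial too small.

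**Working it through.** **The plan's own figures.** Phase 1: 3 × 30 + 30 = 120, as stated. Provisional phase 2: 100 + 100 + 300 + 300 = 800, as stated. The protocol gives no alpha, power, effect size, SD or correlation, so there is no power calculation to reproduce. What follows is illustration.

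**Assumed inputs.** Scores in baseline-SD units with equal variance at both visits; correlation r between baseline and follow-up 1 of 0.5 to 0.8; two-sided alpha 0.05. From the protocol: n = 30 per arm.

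**1. Apparent effect within one arm when the intervention does nothing.** The SD of change is √(2(1 − r)): 1.000, 0.775 and 0.632 at r = 0.5, 0.7 and 0.8. For shared drift d, the noncentrality of a paired t-test is d√30 / √(2(1 − r)), and the critical value on 29 degrees of freedom is 2.045. Example: d = 0.2, r = 0.7 gives 0.2 × 5.477 / 0.775 = 1.414, and a rejection probability of 0.277.

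| Drift (SD) | r = 0.5 | r = 0.7 | r = 0.8 |
|---|---|---|---|
| 0 | 5% | 5% | 5% |
| 0.1 | 8% | 11% | 13% |
| 0.2 | 19% | 28% | 39% |

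Regression to the mean is one possible source of drift. If volunteers enter at an offset from their usual level, it equals offset × (1 − r). An offset of 0 gives 0. Offsets of 0.3-0.5 SD with r = 0.5-0.7 give 0.3 × 0.3 = 0.09 to 0.5 × 0.5 = 0.25 SD, and rejection in 9-26% of arms.

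**2. Phase 2 size if based on change.** n per arm = 2 × (1.960 + 0.842)² / δ² for 80% power. Suppose the true controlled effect is 0.3 SD.
- No drift, δ = 0.3: 15.70 / 0.09 = 174.4, so 175 per arm.
- Drift 0.1, δ = 0.4: 15.70 / 0.16 = 98.1, so 99. Power at the true 0.3: Φ(0.3 × √(99/2) − 1.960) = Φ(0.151) = 56%.
- Drift 0.2, δ = 0.5: 15.70 / 0.25 = 62.8, so 63. Power: Φ(0.3 × √(63/2) − 1.960) = Φ(−0.276) = 39%.

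**3. What the controlled contrast can deliver.** For 30 v 30 with baseline adjustment, SE = √(2(1 − r²)/30): 0.224, 0.184 and 0.155 at r = 0.5, 0.7 and 0.8. The 95% half-width (1.96 × SE) is 0.44, 0.36 and 0.30 SD. Drift that the arms share cancels, so the expected value under no effect is 0.

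**The case against.** Several stronger readings are tempting, and the protocol does not support them.

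- *Phase 1 is judged only by uncontrolled change.* A reader might infer this from the selection rule alone. The analysis section lists within-person change as an additional analysis and plans regression and tests between groups. Change could also be compared between arms. The gap is that the selection rule does not call on that comparison.
- *The change scores decide the primary outcome.* Patient views carry most weight, measures rated unacceptable or irrelevant by more than 25% are excluded, and sensitivity is one input among the top three. EQ-5D-5L is a secondary outcome regardless, and FACIT-F stays for the physical activity trial unless it is unacceptable to more than 25%. Whether an intervention progresses depends on satisfaction, engagement and feasibility, not on change.
- *Regression to the mean is present.* No score threshold governs entry, and interest was declared on an earlier survey. Its size may be zero.
- *Phase 2 will be underpowered.* The provisional sizes are larger than 63 per arm. At 0.3 SD, 100 v 300 has Φ(0.3/√(1/100 + 1/300) − 1.960) = 74% power, and 300 v 300 has 96%. Those sizes are themselves to be revised from phase 1, and section 6.3 does not say outright that it means the within-person changes.

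Two further points stand. No paired test is specified for selection, so the rejection rates describe how misleading change can be, not a written decision rule. And drift equal across instruments in SD units would leave their standardised ranking unchanged; only differing drift would alter it.

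It can also be said that the choice of model belongs in an analysis plan. That is fair for the choice between change scores and covariate adjustment. It does not cover this sentence, because the protocol itself states the estimator.

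**Conclusion.** The point holds, as something that should be fixed. The protocol names a causal quantity, fixes an estimator that does not isolate it, and leaves out the randomised control that would. None of the limits above makes uncontrolled change a valid measure of effectiveness or sensitivity.

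The size is conditional: nil if there is no non-treatment change, and otherwise as tabulated for the assumed drift and correlation. The consequence for phase 2 power also assumes that the within-person figure is what section 6.3 feeds into the sample size. That is the natural reading, since no other definition of phase 1 effectiveness is given, but it is not explicit. The harm would be a less well chosen primary outcome and lost power in phase 2. It would not be a false claim of effect from phase 2, which is the stage at which the objectives place effectiveness.

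**What to change.** In section 6.7 on outcome selection, replace the sentence on short-term effectiveness with:

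> Sensitivity and short-term effect of each measure will be the baseline-adjusted difference between each intervention and randomised control at follow-up 1, divided by the pooled baseline SD, with 95% CI; within-person change is descriptive only.

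In section 6.3, state that any phase 1 effect used to size phase 2 is this controlled estimate, considered with its interval.

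No new data are needed, since baseline scores and controls are already planned. The costs are these:
- Intervals will be wide. With a half-width of 0.30-0.44 SD, the estimate should inform the choice of outcome and the sample size, not decide them.
- The contrast will not fully remove season. The timetable (section 7.9) starts controls and text messages together in May 2023, but enters listening-support participants five a month and runs exercise groups from April and September.
- The timetable refers to later intervention participants who were initially controls. The protocol should confirm that controls stay untreated until follow-up 1; otherwise the contrast is lost.

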#### 6.7 Analysis and outcome measures

Qualitative – The qualitative data will be analysed using thematic analysis and NVivo12 for managing and coding data and follow the criteria for reporting qualitative research (COREQ). Briefly, the stages of analysis involved in our qualitative research involves an inductive-deductive process, including: (i) immersion in the data where transcripts and subsequent coded sections are repeatedly read and discussed by multiple team members to improve reliability, and ensure multiple perspectives and possible interpretations are represented; (ii) a coding (classification) scheme is developed, trialled, discussed and refined, and each line of qualitative data is coded; and (iii) participant extracts for each code are combined. The key themes emerge directly from the data and team discussions, including with multiple patients and clinicians.

Consideration of deviant cases, member checking, triangulation of quantitative and qualitative results and multiple perspectives will be conducted to improve validity.

Quantitative - Transferral of online data from Qualtrics online survey platform and manual data entry, data cleaning, recoding and generation of new variables onto SPSS V26.

Descriptive statistics (means, medians, Interquartile range (IQR), modes and range for continuous data and percentages for categorical data) will be used to describe the demographic, survey and trial data. Contingency tables will be used to describe the multivariate frequency distribution of categorical variables. Bar charts, histograms and boxplots will be used additionally to the above-mentioned statistics and in order to ensure the results are easily accessible to patients, clinicians and policy makers. We will assess the association between variables of interest using Pearson correlation coefficient, T-tests, Wilcoxon-Mann Whitney tests, Chi-Square tests and Kruskal Wallis tests. Regression models will be used to assess the effect of multiple variables on specific outcomes. The within-person change from the baseline to follow-ups and the primary endpoint will also be investigated for each outcome measure. Multiple regression analysis will be used to test differences between groups on multiple measures.

We will also assess the association between pre-defined pairs of variables of interest ) using Pearson correlation coefficient with Chi- Square test. T-tests, Wilcoxon-Mann Whitney tests, Chi-Square tests, Kruskal Wallis tests and one-way/factorial ANOVA will be used appropriately to compare the mean scores, frequencies and impact between groups of patients. Regression models will be used to assess the effect of multiple variables on specific outcomes. As this is a very unexplored area, some additional exploratory analysis will occur in addition to pre-specified measures in order to identify priorities for future research.

Prior to the main analysis, we will conduct data cleaning. Percentages of invalid values, outliers and missing data will be reported. We will also investigate any patterns of missing data. Where appropriate, theoretical and/or clinical criteria will be used to identify invalid values or outliers. Depending on their type and prevalence we will decide on the most appropriate way of addressing. Our options include data exclusion from the rest of the analysis, data replacement with mean or mode values, or data inclusion as separate category (in case of missing data). Our primary option is to conduct "complete-case" analyses. We will not use multiple imputation for missing data. In case of highly prevalent missing data (more than 10% of the sample), sensitivities analyses based on the other option of missing data addressing will be used to assess the robustness of our findings.

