#### Data collection

Baseline survey: On entry into the ADAPT trial prior to being randomised to an intervention or the control group.

Follow-up 1: Baseline + 12 weeks.

Follow-up 2: Baseline + 6 months to more accurately ascertain potential longer-term effects.

In-depth interviews will be carried out with purposively selected participants from questionnaire responses. Interviews will also be carried out during the interventions (in phase 1 only) to assess views of different intervention components, in order to refine the interventions and processes for phase 2.

Analysis	Qualitative - Thematic analysis including using Nvivo 12 software								
	Quantitative – Descriptive and inferential statistics, including multiple regression analysis.								

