#### 6.3 Participant recruitment

For both the phases, patients who expressed an interest in participating in ADAPT at the end of the INSPIRE survey will be emailed with an ADAPT information sheet to confirm continued interest in participating in ADAPT. They will be randomly selected (until trial numbers filled) and then randomly allocated by the study statistician using block randomisation into one of the intervention or control groups. If INSPIRE study participant responses do not generate sufficient ADAPT participant numbers, additional recruitment will be through online advertising via patient charities and support groups and then randomly allocated to intervention groups. If numbers interested in phase 1 exceed study capacity, those participants will be emailed to be informed they were not randomly selected to

participate in phase 1 but will be invited to apply again for phase 2 if interested. Exact sample sizes for phase 2 will be calculated from phase 1 effectiveness result indications. Phase 1 participants will not be eligible for phase 2 participation.

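### The protocol names several between-group tests but does not commit the randomised comparison to adjustment for each instrument's own baseline score

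*Protocol*

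**What the plan says.** **Timing of measurement.** The synopsis (Section 4, Data collection) states: "Baseline survey: On entry into the ADAPT trial prior to being randomised to an intervention or the control group". Follow-ups come at 12 weeks and 6 months after baseline. A pre-randomisation score therefore exists in every arm.

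**Analysis.** Section 6.7 (Analysis and outcome measures) makes three relevant statements:

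- On tests, after listing t-tests, Wilcoxon-Mann-Whitney and chi-square: "Kruskal Wallis tests and one-way/factorial ANOVA will be used appropriately to compare the mean scores, frequencies and impact between groups of patients".
- On baseline: "The within-person change from the baseline to follow-ups and the primary endpoint will also be investigated for each outcome measure".
- On a model: "Multiple regression analysis will be used to test differences between groups on multiple measures". No covariates are listed, and the model is not ranked above the tests.

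**Phase 1 effectiveness.** Section 6.7 (Selection of outcome measures for phase 2) adds: "Short-term effectiveness of each intervention will be measured by using the within-person change from baseline to follow-up one, for each phase 1 instrument". This also shows that each phase 1 instrument is measured at baseline.

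**Size.** Phase 1 has 30 participants in each of three intervention groups and 30 controls. Phase 2 is provisionally 100 (physical activity), 100 (listening support), 300 (text messaging) and 300 (control). Section 6.3 says: "Exact sample sizes for phase 2 will be calculated from phase 1 effectiveness result indications". No significance level, power, effect size, standard deviation or correlation is given.

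**The concern.** The listed two-sample and k-sample tests do not take a continuous baseline score as a covariate. They can be run on raw follow-up scores, which ignores baseline, or on change from baseline, which uses it with a fixed weight of one. In a randomised trial neither is more precise in expectation than regressing the follow-up score on arm and baseline. Change scores are noisier even than ignoring baseline when the correlation is below 0.5.

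The text also offers several non-equivalent analyses of the same contrast, with only a general appeal to appropriateness to choose between them.

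Two things are at stake:

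- **Phase 2**, the effectiveness trial, could report wider intervals than its data allow.
- **Phase 1 effect estimates**, from 30 per arm, are to inform the phase 2 sample size. Without adjustment they carry part of any chance baseline difference between arms.

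**Working it through.** The protocol states no power, so there is no figure to reproduce. What follows is an illustration under assumptions.

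**Inputs from the protocol:** arm sizes of 30 v 30 (phase 1), and 100 v 300 and 300 v 300 (provisional phase 2, with one shared control group).

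**Assumed:** outcome SD of 1 at both times; baseline-to-follow-up correlation r of 0.3, 0.5 or 0.7; two-sided 5% level; normal approximation.

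**Step 1: standard errors, relative to a follow-up-only comparison.**

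- Baseline-adjusted: sqrt(1 - r²)
- Change score: sqrt(2(1 - r))

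| r | Baseline-adjusted | Change score |
|---|---|---|
| 0.3 | sqrt(0.91) = 0.95 | sqrt(1.4) = 1.18 |
| 0.5 | sqrt(0.75) = 0.87 | sqrt(1.0) = 1.00 |
| 0.7 | sqrt(0.51) = 0.71 | sqrt(0.6) = 0.77 |

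The baseline-adjusted column is the smallest in every row. At r = 0.5 the variance ratio of 0.75 equals 1/0.75 = 1.33 times the participants, about a third more.

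**Step 2: power, if the follow-up-only test had 80%.** The effect is then 1.960 + 0.842 = 2.802 unadjusted standard errors. Power with relative standard error k is Φ(2.802/k - 1.960). For r = 0.5, adjusted: 2.802/0.866 - 1.960 = 1.275, and Φ(1.275) = 89.9%.

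| r | Follow-up only | Change score | Baseline-adjusted | Gain over follow-up only | Gain over change score |
|---|---|---|---|---|---|
| 0.3 | 80% | 65.8% | 83.6% | 3.6 points | 17.7 points |
| 0.5 | 80% | 80.0% | 89.9% | 9.9 points | 9.9 points |
| 0.7 | 80% | 95.1% | 97.5% | 17.5 points | 2.4 points |

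These figures do not depend on arm size, because the effect is scaled to give 80%. That effect is 0.72 SD for 30 v 30, 0.32 SD for 100 v 300 and 0.23 SD for 300 v 300. A simulation with t-based tests (8,000 runs per setting) agrees: at r = 0.5, adjusted power is 0.896, 0.902 and 0.904 for the three contrasts.

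**Step 3: sensitivity to the 80% starting point.** With 100 v 300 and an effect of 0.3 SD, power rises from 73.8% to 85.1% at r = 0.5, a gain of 11.3 points. With 0.5 SD it rises from 99.1% to 99.9%, a gain of 0.8 points. The gain in power depends on an effect size the protocol does not give. The standard-error ratio in Step 1 does not.

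**Step 4: chance imbalance in phase 1.** With 30 v 30, the standard error of the baseline difference is sqrt(1/30 + 1/30) = 0.26 SD. An imbalance of that size shifts a follow-up-only difference by r × 0.26, which is 0.13 SD at r = 0.5. It shifts a change-score difference by (r - 1) × 0.26, which is -0.13 SD. Baseline adjustment removes the shift in expectation.

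**Step 5: type I error.** Simulated at 30 v 30, it was 0.044 to 0.050 for all three analyses. The issue is precision, not false positives.

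**The case against.** The strongest reply is that the protocol already allows the right analysis. It names multiple regression for group differences, and the synopsis names multiple regression as its one specific quantitative method. Regressing follow-up on arm plus baseline is one form of that. Covariate lists and the choice of main model are often left to a statistical analysis plan, and one may exist. The sentence listing the tests does not say that its groups are the randomised arms, and it stands close to text on exploratory work.

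Much of this stands. A reader might infer that the protocol analyses follow-up scores without reference to baseline. The documents do not support that: change from baseline is to be examined for every outcome measure, and the listed tests can be run on change scores. A reader might also infer a definite power loss of about 10 points. That figure needs both an assumed correlation of 0.5 and an assumed 80% unadjusted power, and neither is in the protocol. Phase 1 is mainly about acceptability and feasibility. The phase 2 size and primary outcome are still open, and Section 6.1 allows separate trials with separate controls, so there is no planned power to lose.

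What does not stand is that this is only missing detail. The protocol does state its between-group methods. The only use of baseline it spells out is change. The regression permits baseline adjustment but does not commit to it.

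**Conclusion.** The point holds in a limited form. The protocol sets out several between-group analyses, does not say which is the main one, and nowhere puts the baseline score into a between-arm model.

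The firmest measure of what adjustment offers is the standard error: 0.95, 0.87 and 0.71 of the unadjusted value at correlations of 0.3, 0.5 and 0.7. In power terms this is roughly 4 to 17 points over a follow-up-only test that had 80%. The gain over change scores runs the other way, from about 18 points at 0.3 to about 2 at 0.7. All of these rest on assumed correlations and on equal variance at both times. The gain is zero if the planned regression already includes baseline.

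The validity of the tests is not in question. The point matters mainly for phase 2 and for the phase 1 estimates that will inform its size. It is worth correcting because the remedy is free.

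**What to change.** In Section 6.7 (Analysis and outcome measures):

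1. State that the multiple regression already mentioned is the main between-arm analysis for each continuous outcome collected in all arms (RULS-6, Connor-Davidson, GAD-7, PHQ-8, ADAPT, FACIT-F, EQ-5D-5L in phase 1, and those retained in phase 2).
2. Specify the model: follow-up score on randomised arm plus that instrument's own baseline score.
3. Report each intervention-minus-control difference with its 95% interval at follow-up 1 and follow-up 2.
4. Keep the t-tests, Wilcoxon-Mann-Whitney, Kruskal-Wallis and ANOVA for descriptive or non-randomised comparisons. If change within an arm is described, use paired methods.

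It would also help to report the phase 1 baseline-to-follow-up correlations, so that the phase 2 sample size can use an observed value.

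The cost is a change of wording in the protocol or analysis plan. The baseline scores are already collected, SPSS fits the model, and no extra participants or surveys are needed.
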